#### 2 ANALYSIS POPULATIONS

#### 2.1 ANALYSIS POPULATIONS

The primary analysis population will be all eyes that are randomized for the precision of biometric measurements, and all eyes that are randomized and implanted for all other analyses. Mean change in total Meibomian gland score will be compared between study group eyes and control group eyes at 1 month postoperatively. All other key study endpoints will be evaluated at 3 months postoperatively. Additional endpoints will be evaluated at 1 month and 3 months postoperatively for the study group and control group and 4 months postoperatively for crossover control group only. Missing data will not be imputed.

Since both eyes of the same subject will be randomized into the same group, eye-specific measurements of same subject are clustered and likely to be positively correlated. As a subset analysis, right and left eyes of subjects will be analyzed for the key eye-specific study endpoints separately to assess for any differences by eye. Demographics/enrollment/accountability data and binocular data will be reported for all randomized subjects with study IOLs successfully implanted.

Version 1.0 1 SAP/DRYE-102-SELF

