10.2 VISIT SCHEDULE

The study visit schedule for all study subjects is outlined in **Table 1**.

Subjects randomized to the **Study Group** will undergo a minimum of the following four study visits (with visit windows shown in parentheses):

- 1) Preoperative Visit #1, including LipiFlow treatment (may occur on the same day or within 1 week of Visit #1)
- 2) Preoperative Visit #2 (2 - 4 weeks after LipiFlow treatment)
- 3) 1 Month Postop (30 - 60 days after cataract surgery on second eye)
- 4) 3 Months Postop (10 to 14 weeks after cataract surgery on second eye)

Subjects randomized to the **Control group** will undergo a minimum of the following five study visits (with visit windows shown in parentheses):

- 1) Preoperative Visit #1
- 2) Preoperative Visit #2 (2 - 4 weeks after Preoperative Visit #1)
- 3) 1 Month Postop (30-60 days after cataract surgery on second eye)
- 4) 3 Months Postop (10 to 14 weeks after cataract surgery on second eye), including the crossover LipiFlow treatment, which should occur within 0 - 7 days after the 3 months postoperative visit
- 5) 4 Months Postop (4 to 6 weeks after receiving crossover LipiFlow treatment)

Unscheduled visits may be conducted as necessary at the discretion of the investigator for medically-indicated follow-up.

Table 1: Visit Schedule

NAME OF VISIT	GROUPS	PROCEDURES	VISIT WINDOW
Preoperative #1	All	Informed Consent, Screening, Baseline, Randomization and Enrollment	Per site practice
LipiFlow Treatment	Study Group	LipiFlow treatment	LipiFlow treatment can occur on the same day or within 1 week of Visit #1
Preoperative #2	All	Preoperative	Study Group: 2-4 weeks after LipiFlow treatment; Control Group: 2-4 weeks after Visit #1
1 Month Postop	All	1 month postoperative	30-60 days after cataract surgery on second eye
3 Months Postop	All	3 months postoperative; The crossover Control group will receive LipiFlow treatment within 0-7 days after the 3 months postoperative visit	10 to 14 weeks after cataract surgery on second eye
4 Months Postop	Crossover Control Group Only	4 months postoperative	4 to 6 weeks after receiving crossover LipiFlow treatment

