If the LipiFlow treatment is performed on the same day as Preoperative Visit #1, the medical/ophthalmic history and slit lamp evaluation do not need to be repeated before treatment. In this case, the Investigator must review the baseline history and slit lamp exam information prior to treatment to ensure no contraindication to LipiFlow treatment is present. If the LipiFlow treatment visit is performed on a different day from Preoperative visit #1, the Investigator or designee documents any changes to medical/ophthalmic history and performs a slit lamp evaluation to determine if an ocular adverse event is present prior to treatment. If the subject has an active ocular adverse event, the LipiFlow treatment should not be performed at this visit.

The Investigator or designee cleans the lid margin (**Appendix E**) and then performs treatment with the LipiFlow system per the LipiFlow System Instructions for Use. The Investigator documents any problems with the LipiFlow system during treatment. The Sponsor will investigate any reported problem with the LipiFlow system.

The Investigator or designee performs slit-lamp evaluation after LipiFlow treatment to check for any adverse events. At the completion of the exam, the subject is instructed on how to perform blinking exercises (**Appendix F**) for 1 month after treatment to facilitate the flow of oils from the meibomian glands into the tear film. The subject is advised to return for Pre-Operative Visit #2, which must be scheduled 2 - 4 weeks after the LipiFlow treatment.

At the completion of Preoperative Visit #1, the subject is reminded not to use any MGD or dry eye prescription medications or other treatments during the study (except for pre-existing OTC artificial tears, ocular lubricants, ointments, emollients or ω-3 dietary supplements). The dosage and frequency of any pre-existing use of OTC products upon study entry must be documented in the subject's medical record and in the study case report forms. Except for LipiFlow treatment, no other MGD or dry eye treatment is prescribed or administered to subjects throughout the study.

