10.6 POSTOPERATIVE PROCEDURES

Postoperatively, subjects will be examined according to the schedule in Section 10.2, Visit Schedule. The most recently operated eye will be evaluated at the 1-day and 1-week visits per site practice standard of care. Both eyes will be evaluated for all the subjects at the 1-month and 3-month visits. For the subjects in Control group, both eyes will receive crossover LipiFlow treatment within 0 - 7 days after the 3-month postoperative visit, and will be evaluated at the 4-month visit.

To maintain consistency throughout the study, it is recommended that a single individual (study technician or coordinator designated by the investigator) conduct all postoperative study-related vision testing. In addition, a back-up person should also be designated and trained.

NOTE 1: No additional refractive procedures are to be performed during the operative or postoperative study period (e.g., Limbal-Relaxing Incisions (LRIs), PRK, LASIK or LASEK).

NOTE 2: If the subject chooses to wear contact lenses after the cataract surgeries, they must be removed prior to any postoperative visits and prior to any LipiFlow treatment. The subject may resume contact lens wear one hour after completion of treatment or per site standard of practice.

NOTE 3: If the subject is implanted with a TECNIS Symfony IOL only in the first eye, the subject will be followed for monocular testing only until study exit for that first eye. The fellow eye will be considered exited as of the second operative date. Both eyes may still receive the LipiFlow treatment if the subject was randomized to the Control group.

POSTOPERATIVE EXAMINATION PROCEDURES

Postoperative examinations will be conducted 1 and 3 months after second-eye cataract surgery for all subjects, and at 4 months for Control group subjects only. General descriptions and requirements of the various tests are provided in **Appendix D**. The postoperative case report form (CRF) will collect the following information, although not all information is required at every visit (see **Appendix B**):

MANIFEST REFRACTION AND REFRACTION ADJUSTMENTS

Postoperative study manifest refractions are to be performed using the M&S System at a distance of 4.0 meters. Manifest refraction (MR) is to be performed using the Maximum Plus refraction method as detailed in **Appendix M**.

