17. RISK ANALYSIS

POTENTIAL RISKS AND RISK MANAGEMENT

RISKS ASSOCIATED WITH USE OF LIPIFLOW

The use of the LipiFlow System in this study is non-significant risk. No device-related serious adverse events are anticipated with the use of the LipiFlow system. Transient, non-serious adverse events which may result from the use of the LipiFlow system include, but are not limited to, the onset or increase in the following ocular signs or symptoms that are either 1) clinically significant as determined by the Investigator, or 2) require medical treatment for resolution:

- Eyelid/eye pain requiring discontinuation of the treatment procedure;
- Eyelid irritation or inflammation (e.g., edema, bruising, blood blister, dermatitis, hordeolum or chalazion);
- Ocular surface irritation or inflammation (e.g., corneal abrasion, conjunctival edema or conjunctival injection/hyperemia); and
- Ocular symptoms (e.g., burning, stinging, tearing, itching, discharge, redness, foreign body sensation, visual disturbance, sensitivity to light).

GENERAL RISKS OF CATARACT SURGERY AND IOL IMPLANTATION

There are risks and complications associated with cataract surgery and IOL implantation in general. These can include worsening of vision, hemorrhage, loss of corneal clarity, inflammation, infections, retinal detachment, pupil changes, glaucoma, etc. Complications can result in poor vision, loss of vision or loss of the eye.

RISK MANAGEMENT

Subjects will be closely monitored thought the trial duration. The occurrence of adverse events and complaints will be assessed at each study visit and reported to JJSV according to Section 11.0, Adverse Events and Product Complaints.

Additionally, JSJV will monitor incoming data following the procedures outlined in Section 15.0, Monitoring. The Medical Monitor will ensure subjects are not exposed to additional risks by monitoring serious adverse events, device-related adverse events, and device-deficiencies that could have led to serious adverse events (Section 15.3, Safety Monitoring).

POTENTIAL BENEFITS

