#### 4.2.4 RATE OF ADVERSE EVENTS/MEDICAL AND/OR LENS FINDINGS

The frequency and proportion of eyes with optical/visual, medical and lens complications will be reported over time. The type and rates of adverse events will be summarized for both study group eyes and control group eyes.

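### The planned adverse event rate counts only implanted eyes, so eyes that received LipiFlow but no study lens are left out of it

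*SAP*

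**What the plan says.** SAP 2.1 defines two sets. All randomized eyes serve for biometric precision; the second set is "all eyes that are randomized and implanted for all other analyses". Protocol 20.1 repeats the rule and the synopsis agrees.

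On adverse events, SAP 4.2.4 says: "The type and rates of adverse events will be summarized for both study group eyes and control group eyes". SAP Appendix I lists that table as n and % of eyes. Neither place names a safety or as-treated set.

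In the Study group, LipiFlow is given on the day of Preoperative Visit #1 or within a week of it. Preoperative Visit #2 follows two to four weeks after treatment (Protocol 10.2), and surgery comes later. Adverse events are looked for from the start: at the LipiFlow visit the investigator or designee "performs slit-lamp evaluation after LipiFlow treatment to check for any adverse events" (Protocol 10.3), and Appendix B schedules adverse event collection at that visit and at Preoperative Visit #2.

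Protocol 17 introduces the expected LipiFlow events with "Transient, non-serious adverse events which may result from the use of the LipiFlow system include, but are not limited to". The first item is "Eyelid/eye pain requiring discontinuation of the treatment procedure".

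For a subject implanted in the first eye only, Note 3 of Protocol 10.6 says: "The fellow eye will be considered exited as of the second operative date". It then adds: "Both eyes may still receive the LipiFlow treatment if the subject was randomized to the Control group".

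**The concern.** LipiFlow is the intervention under evaluation, so its adverse event rate should rest on the eyes that received it. In the Study group, receiving a lens happens after LipiFlow. Restricting the rate to implanted eyes therefore selects on something that follows treatment. If a LipiFlow event contributes to a subject not going on to surgery, both the event and the treated eyes leave the table.

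The Control fellow eye in Note 3 is a different problem with the same result: an eye can be treated with LipiFlow and not be counted. At stake is whether the published LipiFlow event rate describes everyone treated or only those who went on to receive a study lens.

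**Working it through.** **1. Which set covers adverse events.** The SAP 2.1 rule is closed: one named exception, then everything else. The adverse event rate is a listed endpoint (Protocol 6.2), and neither SAP 4.2.4, Appendix I nor Protocol 20.3 overrides the rule. Read as written, the denominator is randomized and implanted eyes.

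**2. Whether treated, non-implanted eyes can occur.** The protocol foresees three routes.
- Protocol 10.3 classes subjects who qualify but decide against surgery as screen failures and exits them. It makes no exception for those already given LipiFlow.
- Protocol 10.7 has a category for randomized subjects discontinued prior to treatment. One listed reason is an implant aborted for surgical complications, which in a Study subject would come after LipiFlow.
- Note 3 of Protocol 10.6 exits a non-implanted fellow eye. In the Study group that eye has already been treated.

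**3. The Control fellow eye.** It is exited at the second operative date. Crossover LipiFlow comes within 0 to 7 days after the 3-month visit, which is 10 to 14 weeks after second-eye surgery. Exit precedes LipiFlow, so LipiFlow cannot have caused the non-implantation. The eye is simply missing from the denominator.

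**4. The plan's own attrition figure.** SAP 5 and Protocol 20.5 inflate 55 per group for 20% screen failure or drop-out: 55 / (1 − 0.20) = 68.75, rounded up to 69. This reproduces. It gives 2 × 69 = 138 Study eyes.

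**5. Size, as an illustration.** The documents give no adverse event rate and no rate of leaving between LipiFlow and implantation, so every input except the 69 is assumed. Let N = 138 treated eyes, L = eyes that leave without a lens, p_s = event rate in eyes that stay (5%), and p_l = event rate in eyes that leave.

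- Planned (implanted-only) rate = p_s
- All-treated rate = [(N − L) × p_s + L × p_l] / N
- Understatement = (L / N) × (p_l − p_s)

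Taking 2%, 5%, 10% and 20% of 69 subjects, rounded, gives 1, 3, 7 and 14 subjects leaving, or 2, 6, 14 and 28 eyes.

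| Eyes leaving (of 138) | Planned rate | All treated, p_l = 5% | All treated, p_l = 20% | All treated, p_l = 50% |
|---|---|---|---|---|
| 2 | 5.0% | 5.0% | 5.2% | 5.7% |
| 6 | 5.0% | 5.0% | 5.7% | 7.0% |
| 14 | 5.0% | 5.0% | 6.5% | 9.6% |
| 28 | 5.0% | 5.0% | 8.0% | 14.1% |

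Top row, p_l = 20%: (136 × 0.05 + 2 × 0.20) / 138 = 7.2 / 138 = 5.2%. Bottom row, p_l = 50%: (110 × 0.05 + 28 × 0.50) / 138 = 19.5 / 138 = 14.1%, an understatement of about 9 percentage points.

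The 28-eye row uses the whole 20% allowance. That allowance also covers screen failures and postoperative losses, so the row is an upper case. If leavers had no events at all, the sign would reverse: 110 × 0.05 / 138 = 4.0%, below the planned 5.0%.

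**The case against.** The strongest reply is that safety does not depend on this denominator. Adverse events are assessed at every visit (Protocol 10.6) and are reportable whatever their severity or attribution (11.3). Those serious or device-related are followed until resolution (11.5) and reviewed by the medical monitor (15.3). LipiFlow is a cleared device used within its indication, and the expected events are transient and non-serious, so they do not obviously lead to cancelled surgery. The adverse event rate is a descriptive secondary endpoint with no test or success criterion. The SAP also calls its set primary, which might leave room for another.

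Most of this stands, and it limits the severity. No primary conclusion changes, and the number of eyes affected may be small. It does not cure the wording: no other set is defined, and recording an event does not put it into a rate whose population excludes the eye.

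A reader might go further and infer that these events are lost, or that a fellow eye called exited goes unexamined when it is given LipiFlow. The documents do not support that. Note 3 limits the subject to monocular testing, but the reporting rules above still apply, and Appendix B (note a) requires a slit-lamp examination before and after LipiFlow. The gap is in the summarised rate.

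**Conclusion.** The point holds as a population error in the summary of adverse events and should be fixed. As written, LipiFlow-treated eyes without a study lens are outside the adverse event rate in both groups: in the Study group through a condition that follows treatment, in the Control group through omission.

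Under the assumed inputs, the understatement runs from zero to about 9 percentage points. It is zero when leavers and stayers have the same event rate, and reaches the top only if 28 of 138 eyes leave with a 50% event rate.

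A reader might infer that the planned rate is necessarily too low, or picture a table showing no events because every affected subject left. Neither follows. Protocol 17 makes it plausible that some events interrupt treatment, but the documents do not show that treated eyes that leave have more events than those that stay. Size and direction cannot be known from the documents. Nor is a confidence limit planned for this table.

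**What to change.** In SAP 2.1 and 4.2.4 and in Protocol 20.1, give adverse events their own population:
- Summarise adverse events in all randomized subjects.
- For LipiFlow-related events, use as denominator every eye in which LipiFlow was started, implanted or not.
- Keep the implanted-eye set for lens findings and efficacy.

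Add the LipiFlow-treated denominator to the adverse event row of SAP Appendix I. In Note 3 of Protocol 10.6, the statement that the fellow eye is exited and the statement that both eyes may still receive LipiFlow must be reconciled with each other and with adverse event reporting. How such an eye is followed clinically is for the sponsor to decide.

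The cost is wording in two documents and one table specification. The preoperative adverse event data are already collected, and the change to the analysis set needs no extra subjects or visits. The downside is that the reported LipiFlow rate may be slightly less favourable.

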- Mean MRSE at 4 months postoperative compared to target MRSE
- Percent of eyes with MRSE within 0.50 D and within 1.00 D of target MRSE at 4 months postoperative
- Contrast acuity at 4 months postoperative compared to 3-month.
- Mean change in total meibomian gland score from 3 months to 4 months postoperative.
- Mean change in total SPEED score from 3 months to 4 months postoperative.
- Rates of adverse events in the Study and Control groups.
- Rates of medical and/or lens findings in the Study and Control groups.

STUDY VISITS AND PROCEDURES:

Inclusion and exclusion qualifications will be assessed at the start of Preoperative Visit #1 according to the protocol criteria. The Informed Consent Document and Authorization for Use/Disclosure of Health Information form (HIPAA authorization) must be signed by any subjects who agree to participate in the study prior to undergoing any study-specific procedures. After determination that all inclusion/exclusion criteria have been met, enrolled subjects will be randomized to either Study group or Control group in a 1:1 ratio.

Study visit schedule, procedures and key data collected at each visit are shown in **Appendix A, Appendix B, and Section 10.2, Visit Schedule, Table 1.**

DATA ANALYSIS:

Key study endpoints are the comparisons between study group and control group for precision of biometric measurements preoperatively, mean change in total Meibomian gland score at 1 month postoperatively, mean monocular UCDVA at 3 months postoperatively, rate of refractive predictability at 3 months postoperatively and rate of directed reported ocular symptoms at 3 months postoperatively. Additional endpoints will be evaluated at 1 and 3 months postoperatively for the both groups and 4 months postoperatively for crossover Control group.

Visual acuity data will be converted to LogMAR values prior to analysis. Comparisons between study group and control group for the mean monocular UCDVA at 3 months postoperatively will be performed using one-sided two-sample t-tests with alpha set at 0.05. Precision of preoperative biometric measurements is defined as the average of the three computed standard deviations from each preoperative visit. The Study group is expected to have better total Meibomian gland score at 1 month postoperatively compared to the Control group, and to have better

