20.5 SAMPLE SIZE CALCULATIONS

The sample size determination is based on the primary endpoint of uncorrected distance visual acuity (UCDVA). There is 90% power to detect a 1-line or greater difference in mean UCDVA between the treatment and control groups with 55 subjects in each group. This assumes one-sided two-sample t-test with an alpha of 0.05 and standard deviation of 1.6 lines. Adding 20% screen failure/drop-out rate will require enrolling 69 subjects per group.

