APPENDIX A DIAGRAM OF STUDY FLOW

APPENDIX B SUMMARY OF PROCEDURES REQUIRED AT EACH VISIT

Examination	Preop Visit #1	LF Tx ^d (Study Group Only)	Preop Visit #2 ^e	Operative	1-Mo. Post-op	3-Mo. Post-op and Crossover LF Tx ^f	4-Mo. Post-op (Crossover Group Only)
Informed consent, medical and ocular history, inclusion/exclusion criteria	X						
Potential visual acuity, targeted refraction, IOL power calculations, corneal topography	X		X				
IOL power/serial number, Toric power/axis (if needed)				X			
Monocular UCDVA, BCDVA	X ^c				X	X	X
Binocular UCDVA, BCDVA					X	X	X
Binocular UCIVA and UCNVA						X	X
Manifest refraction	X ^c				X	X	X
Contrast acuity testing (binocular, 10% contrast acuity and 20/40 contrast threshold)						X	X
Keratometry, biometry (repeat 3 sets of biometry / keratometry measurements)	X		X				
Meibomian gland assessment	X				X	X	X
Ocular surface staining	X		X		X		
TBUT	X		X		X		
Eyelid margin evaluation	X		X		X		
Meibomian gland imaging (LipiScan or LipiView II)	X				X		X
Biomicroscopic slit-lamp exam ^a	X	X	X		X	X	X
Fundus exam ^b	X						
Adverse events	X	X	X		X	X	X
Ocular and systemic medications	X	X	X		X	X	X
Ocular/Visual symptom assessment (non-directed)	X		X		X	X	X
SPEED and PRVSQ questionnaires	X		X			X	X

^a Includes determination of medical and lens findings/complications, lens orientation. Slit-lamp exam is performed both before and after LipiFlow treatment.

^b Fundus exam may be performed dilated with ophthalmoscopy or undilated per site practice standard of care.

^c Preoperative UCDVA, BCDVA and refraction tests will be performed per site practice standard of care.

^d Preoperative LipiFlow treatment can occur the same day or within 1 week of Preoperative Visit #1.

^e Preoperative Visit #2 will be 2-4 weeks after LipiFlow treatment for study group and be 2-4 weeks after the Preoperative Visit #1 for control group.

^f LipiFlow treatment after 3 months postop exams for the Crossover Control group only.

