#### 1 INTRODUCTION

This document summarizes the statistical methods to be implemented during the analysis of data for the evaluation LipiFlow treatment in cataract surgery practice. This is a post-market, prospective, randomized, multi-center, bilateral, open-label, cross-over, comparative clinical study. Up to 140 subjects will be randomized and bilaterally implanted to achieve approximately 110 evaluable subjects (55 in the study arm and 55 in the control arm).

The purpose of this study is to evaluate the LipiFlow treatment in adult patients with mild to moderate Meibomian gland dysfunction (MGD) undergoing bilateral cataract surgery in terms of preoperative surgical planning and postoperative outcomes including refractive outcomes, visual outcomes and ocular comfort.

The key study endpoints are the comparisons between study group and control group for precision of biometric measurements preoperatively, mean change in total Meibomian gland score at 1 month postoperatively, mean monocular UCDVA at 3 months postoperatively, rate of refractive predictability at 3 months postoperatively and rate of bothersome ocular symptoms at 3 months postoperatively. Additional endpoints will be evaluated at 1 month and 3 months postoperatively for the both groups and 4 months postoperatively for crossover control group.

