#### 5 SAMPLE SIZE CALCULATIONS

The sample size determination is based on the primary endpoint of uncorrected distance visual acuity (UCDVA). There is over 90% power to detect a 1-line or greater difference in mean UCDVA between the treatment and control groups with 55 subjects in each group. This assumes one-sided two-sample t-test with an alpha of 0.05 and standard deviation of 1.6 lines. Adding 20% screen failure/drop-out rate will require enrolling 69 subjects per group.

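### The 3-month UCDVA success test uses only eyes seen at 3 months, ignores the 1-month UCDVA and has no missing-data sensitivity analysis; loss that depends on acuity differently by arm would bias it either way

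*SAP*

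**What the plan says.** - **Missing data.** SAP 2.1, and protocol 20.1 in the same terms: "Missing data will not be imputed". The UCDVA analysis population is "all eyes that are randomized and implanted for all other analyses" (SAP 2.1).
- **Test.** The protocol Synopsis (Data Analysis) says the 3-month monocular UCDVA comparison "will be performed using one-sided two-sample t-tests with alpha set at 0.05". SAP 4.1.1 gives only the criterion, p ≤ 0.05 in favour of the Study group, and names no model. Of the key endpoints, only this one carries a success criterion.
- **Loss allowed for.** SAP 1: "Up to 140 subjects will be randomized and bilaterally implanted to achieve approximately 110 evaluable subjects". SAP 5 and protocol 20.5 add 20% for screen failure and drop-out together, taking 55 per group to 69.
- **Data collected.** The Appendix B row "Monocular UCDVA, BCDVA" is marked at 1 month as well as 3 months, and protocol 10.6 has both eyes examined at each of these visits. No section of the SAP and no entry in its table listing brings the 1-month UCDVA into the 3-month comparison.
- **What exists for missing visits.** The SAP reports counts (2.2, 3.1). The protocol has follow-up duties (10.7) and prevention measures (15.1). Neither document names a missing-data sensitivity analysis.

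**The concern.** A two-sample t-test on the eyes seen at 3 months estimates the right difference only if loss is unrelated to acuity, or related to it in the same way in both arms. Two features make it unsafe to take that for granted. First, subjects with poor results can leave: protocol 10.7 exits subjects whose study lenses are removed and counts refusal of further participation as loss. Second, the trial is open-label and the reason to attend at 3 months differs by arm, because controls receive their LipiFlow treatment after that visit and Study subjects have no treatment pending.

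At stake is the size of the UCDVA difference and the one-sided 5% error of the trial's only formal success test. The plan collects an early value of the same outcome that could correct much of this, and leaves it out.

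**Working it through.** **1. The plan's own figures.** Inputs from SAP 5: 55 per group, difference 1 line, SD 1.6 lines, one-sided alpha 0.05 ("This assumes one-sided two-sample t-test with an alpha of 0.05 and standard deviation of 1.6 lines").
- SE = 1.6 × √(2/55) = 0.305 line.
- Power ≈ Φ(1/0.305 − 1.645) = 94.9%, or 94.7% with the noncentral t. This agrees with the SAP's "over 90% power to detect a 1-line or greater difference in mean UCDVA".
- 55/(1 − 0.20) = 68.75, so 69 per group, as stated.

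**2. Size of the allowed loss.** 30/140 = 21.4% (SAP 1); 14/69 = 20.3% (SAP 5). The 20% includes screen failure. Protocol 10.7 places screen failure before randomization, and 10.3 also counts those who qualify but decline surgery. Evaluable is not defined. So 20–21% is an upper figure for loss after implantation, and I also show 10%.

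**3. Bias of the available-eye test.** Assumptions not in the documents: 70 per arm with a 1-month value; subject-level SD 1.6 lines at both visits; correlation ρ of 0.5–0.8 between visits; no true effect; the same loss rate f in both arms, random in Control; in Study, logit P(lost) = a + s·z, where z is the standardized 1-month LogMAR (higher is worse) and a is set to give f overall.
- Bias in favour of Study = −1.6 × ρ × E[z | seen at 3 months].
- One-sided error ≈ 1 − Φ(1.645 − bias/SE), with SE = 1.6 × √(2/n) and n seen per arm.

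| f (n per arm) | s | a | E[z given seen] | Bias, ρ 0.5 to 0.8 (lines) | SE | Error |
|---|---|---|---|---|---|---|
| 10% (63) | 0.7 | −2.385 | −0.0668 | 0.05 to 0.09 | 0.285 | 7.2 to 8.9% |
| 21.4% (55) | 0.2 | −1.311 | −0.0426 | 0.03 to 0.05 | 0.305 | 6.3 to 7.1% |
| 21.4% (55) | 0.7 | −1.429 | −0.1388 | 0.11 to 0.18 | 0.305 | 10.0 to 14.4% |
| 21.4% (55) | −0.7 | −1.429 | +0.1388 | −0.11 to −0.18 | 0.305 | 2.2 to 1.3% |
| 21.4% (55) | 0.7 in both arms | −1.429 | equal | 0 | 0.305 | 5% |

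Example, third row: 1.6 × 0.8 × 0.1388 = 0.178; 0.178/0.305 = 0.58; 1 − Φ(1.645 − 0.58) = 14.4%.

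A simulation of 8,000 trials per setting at ρ of 0.5 and 0.8 agrees for s = ±0.7. Error was 6.9–8.9% at 10% loss, 10.3–14.1% at 21.4% loss, 1.2–2.3% with the slope reversed at 21.4% loss, and 4.7–5.2% with equal slopes. In the same trials, the likelihood estimator that uses the 1-month value had bias within 0.005 line and error of 4.7–5.3%. That estimator used one eye per subject.

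**4. Unequal loss rates.** With the same slope of 0.7 but 21.4% loss in Study and 10% in Control, bias is 1.6 × ρ × (0.1388 − 0.0668), or 0.06–0.09 line.

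**5. Precision.** With random loss, using the 1-month value multiplies the variance by 1 − (15/70)ρ², which is 0.946, 0.895 and 0.863 at ρ of 0.5, 0.7 and 0.8. The SE falls by 2.7%, 5.4% and 7.1%, and effective n per arm (55 divided by the factor) is 58.1, 61.5 and 63.7. One-sided power goes from 94.7% to 95.6%, 96.4% and 96.9%.

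**The case against.** **The loss may be small or badly placed for the fix.** Part of the 20% never reaches surgery, and subjects lost before 1 month have no value to borrow. This stands. If half of a 22% loss occurs at random before the 1-month visit, the error at slope 0.7 is 7.7–10.1%; with 5% loss in total it is 6.0–6.6%. The 21% rows are therefore an upper case.

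**The dropout slope is chosen, not documented.** This also stands. A reader might infer that Study subjects with poor acuity will leave and that LipiFlow will be overstated. Nothing in the documents says so. The pending control treatment suggests different attendance by arm, not which eyes go missing, and the reverse slope works against LipiFlow. The finding is that the test is unprotected, not that it leans one way.

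**The loss is already in the sample size.** A reader might infer that the trial is underpowered because of missing eyes. It is not: 55 per arm gives 94.7% one-sided power, and the 1-month data add only 1 to 2 points. Extra enrolment does not remove bias, however.

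**Not imputing is not the fault.** That sentence does not forbid a likelihood model, which imputes nothing. It is the single-visit t-test that discards the 1-month value.

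**Prevention and counts are planned.** They help limit and describe the loss, but they do not test how far the result depends on it.

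**Conclusion.** The point holds as a weakness of the primary analysis that should be corrected. The test uses available eyes only, has no sensitivity analysis, and omits an early measurement of the same outcome that the protocol already requires.

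The consequence is conditional. It arises only if loss is related to acuity and this differs by arm, in slope or in rate. Under the stated assumptions (ρ 0.5–0.8, Study-only slope 0.7, all loss after 1 month), bias is about 0.05–0.09 line at 10% loss and 0.11–0.18 line at 21%, against a design difference of 1 line. One-sided error is 7–9% and 10–14% respectively. The reverse slope gives about 1–2% at 21% loss, and equal dropout patterns give no bias. It would be too strong to say that the plan fails to hold its 5% error, or that 21% of implanted subjects will be lost; the documents support neither. Precision is a minor argument.

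**What to change.** **SAP 4.1.1.** Make the primary analysis a likelihood-based repeated-measures model of LogMAR monocular UCDVA at 1 and 3 months, both eyes, with arm, visit, arm-by-visit and site. Test the 3-month arm contrast at the same one-sided 0.05. Use an unstructured covariance across eye and visit within subject, or subject and eye-within-subject effects with robust standard errors clustered on subject. A single subject effect is not enough, because it forces one correlation across eyes and visits. In a check with inter-eye and between-visit correlations of 0.5, its mean model SE was 0.25 against an empirical 0.28. Keep the available-eye t-test as supportive.

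**Sensitivity analysis.** Add a tipping-point analysis that shifts the missing 3-month values by arm until the conclusion changes. This normally assigns values to missing outcomes, so reword the no-imputation sentence in SAP 2.1 (and protocol 20.1) to allow it for this analysis only.

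**Cost.** SAP text and modest programming, with no new data or visits, settled before 3-month results by arm are examined. The model relies on data being missing at random given 1-month acuity, which is weaker than what the t-test needs but still untestable; the tipping-point analysis covers that. Subjects lost before the 1-month visit gain little.
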